### 1.3.2. Study Rationale

The clinical investigation of PF-06741086 will continue with study B7841002, an open-label, Phase 1b/2, multiple ascending dose (MAD) study in severe hemophilia A or B subjects, including subjects with inhibitors to factor VIII or factor IX. The clinical risk/benefit profile for this population is considered appropriate for the evaluation of safety, tolerability, PK, PD, and efficacy of multiple doses of PF-06741086. Frequency of bleeding episodes (of study subjects during treatment with PF-06741086) will be compared against the frequency of bleeding episodes in an external control group as a measure of therapeutic efficacy.

The primary objective of study B7841002 is to evaluate the safety and tolerability of multiple ascending doses of PF-06741086 administered by the SC or IV route. Secondary objectives include evaluating the PK and PD properties of PF-06741086, as well as assessing clinical efficacy based on the frequency of bleeding episodes. Selection of the PD endpoints and sampling schedule are based on results from non-clinical studies and the Phase 1 FIH study results. They will reflect either target binding by PF-06741086 (ie, TFPI level) or downstream pharmacologic effects of TFPI inhibition (ie, dPT, TGA, PF1+2 and D-dimer). Thrombosis is a potential risk for inhibition of TFPI, and PF-06741086 is expected to significantly inhibit TFPI, particularly at the highest dose levels. To minimize this risk, hemophilia patients with a known history of thrombotic, ischemic or coronary artery disease, or known pro-thrombotic conditions (eg, Protein C deficiency) will be excluded from this study. Safety monitoring will include laboratory parameters that may be modulated due to coagulopathy (eg, [PT]/INR, aPTT, fibrinogen, ATIII and platelet counts) and parameters to screen for possible thrombotic events (eg, cardiac troponin I). Laboratory endpoints to detect excessive modulation of the coagulation pathway will be monitored during the period of peak drug exposure, until at least 28 days have passed since the final administration.

Potential risks for treatment with PF-06741086 are thrombi or emboli. Depending on location and severity, thrombi or emboli may be life threatening or fatal. An additional potential risk for treatment with PF-06741086 is ADA-induced hypersensitivity.

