### **3.2. Study Duration**

Subjects will be screened within 35 days prior to administration of the investigational product to confirm that they meet the subject eligibility criteria for the study. At the Day 1 clinic visit, eligibility criteria will be confirmed. Subjects will begin dosing on Day 1. Subjects will be required to return to the clinic (eg, study site) for PK/PD sample collection on Day 2 and Day 4. Subjects will then be required to attend weekly clinic visits on Day 8, Day 15, Day 22, and Day 29. For subjects with once weekly (QW) dosing frequency, investigational product will be administered at these visits as well.

Following Day 29, provided that safety was confirmed for the cohort and no stopping criteria were met, all subjects in each cohort will return to the clinic for PK/PD sample collection on Day 30 and Day 33. Subjects in the SC cohorts will receive treatment on Day 36, Day 43, Day 50, Day 57, Day 64, Day 71, Day 78, follow-up on Day 85, and end-of-study procedures on Day 113. For the Day 36, 43, 50, 64, 71 and 78 SC treatments, in countries where approved by respective competent authorities and at sites where it is approved by the respective IRB/EC, SC treatment with investigational product may be administered by investigator site personnel in a home care or ambulatory clinic setting. Subjects in the IV cohort will receive treatment on Day 57, follow-up on Day 85, and end-of-study procedures on Day 113.

Subjects with positive ADA or NAb results may be requested to return for additional follow-up visits after Day 113.

Subjects who experience a treatment-related adverse event (including lab abnormalities) at any time point will continue to be followed through resolution or stabilization of the event as agreed upon by the investigator and Sponsor.

The maximum total duration of the study for a single subject, from initial screening to final follow-up, will be approximately 5 months.

During the study data will be reviewed on an ongoing basis to determine if PF-06741086 is safe and tolerated. Dosing of subjects in any cohort may be stopped if the B7841002 protocol-specified stopping criteria are met ([Section 3.3](#)). If available data are permissive for dose progression, subjects will be recruited into the next cohort in the study and dosed at the next dose level of PF-06741086.

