### **Dose Modifications**

Any subject who experiences a dose limiting toxicity (per [Appendix 2](#)) will be discontinued from treatment with the investigational product and will be followed for adverse event monitoring until resolution of the respective toxicity and elimination of study drug or the end of the study (Day 113) and resolution or stabilization of the respective toxicity, whichever occurs first. In addition, subjects who have not experienced dose limiting toxicities but are currently receiving a dose that met the dose limiting toxicities criteria for termination of dose escalation as defined in [Section 3.3](#) will be removed from the current dose level and dropped to the next lowest exposure level.

Subjects who have not experienced a dose-limiting toxicity may also require dose modifications. Criteria for modifications of dosing in an individual subject are as follows:

- Moderate severity infusion/injection site reactions at more than 2 consecutive visits (eg, Day 22, Day 29, and Day 36);
- Treatment emergent adverse event(s) that increases in severity/grade, without resolution, (eg, Mild to Moderate and continuing) after repeat administration of PF-06741086;

- Treatment emergent adverse event(s) of any severity with more than 2 occurrences following repeat administration of PF-06741086.

Any subject who meets the above criteria during treatment with PF-06741086 will be removed from the current dose level and dropped to the next lowest exposure level, unless the event(s) are incontrovertibly due to extraneous causes or are incontrovertibly complications of hemophilia (see [Section 8.6](#) for qualifying events).

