### 5.7.1. Prohibited Medications

Factor VIII (within 72 hours) or Factor IX replacement therapy (within 96 hours), or bypass agent therapy (FVIIa or APCC: within 72 hours), before Screening is prohibited. Depending on the coagulation factor product in use, additional wash out time may be required prior to the screening assessments to achieve a factor activity level  $\leq 1\%$ . If a subject experiences an acute bleeding episode during this washout period requiring treatment with a Factor VIII or IX replacement therapy, or bypass agent therapy, the subject is to be stabilized utilizing this regimen and a new washout period should be initiated. The regimen used to treat the episode should be recorded as a prior medication.

Factor VIII (within 72 hours) or Factor IX replacement therapy (within 96 hours), or bypass agent therapy (for FVIIa or APCC: at least 72 hours), before Day 1 treatment is also prohibited. If a subject experiences an acute bleeding episode during this washout period requiring treatment with a Factor VIII or IX replacement therapy, or bypass agent therapy, the subject is to be stabilized utilizing this regimen and a new washout period should be initiated. The regimen used to treat the episode should be recorded as a concomitant medication. All acute bleeding episodes between Screening and Day 1 must be recorded.

Treatment with rFVIIa **at a dose level greater than approximately 90  $\mu\text{g}/\text{kg}$  is prohibited throughout the study**. If a subject receiving investigational product is subsequently administered a rFVIIa dose greater than approximately 90  $\mu\text{g}/\text{kg}$ , the investigator must immediately contact the Sponsor's medical monitor to discuss the case to determine if the respective subject should continue to receive IP, remain in the study, or be withdrawn immediately.

**Treatment with APCC (eg, FEIBA) is prohibited throughout the study.** Subjects receiving such therapy, who cannot substitute treatment with rFVIIa, at the 90  $\mu\text{g}/\text{kg}$  per dose are not to be enrolled into this study. Subjects who are treated with investigational product who are subsequently administered APCC therapy must be withdrawn from treatment with investigational product immediately. These subjects should be followed at all remaining clinic visits up to Day 113 to monitor for adverse events and any additional safety concerns.

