#### **6.4. Subject Withdrawal**

Withdrawal of consent: Subjects who request to discontinue study treatment will remain in the study and must continue to be followed for protocol specified follow-up procedures. The only exception to this is when a subject specifically withdraws consent for any further contact with him or persons previously authorized by the subject to provide this information. Subjects should notify the investigator in writing of the decision to withdraw consent from future follow-up, whenever possible. The withdrawal of consent should be explained in detail in the medical records by the investigator, as to whether the withdrawal is only from further receipt of investigational product or also from study procedures and/or post treatment study follow-up, and entered on the appropriate case report form (CRF) page. Publicly available information should be used to determine vital status only as appropriately directed in accordance with local law.

Lost to follow-up: All reasonable efforts must be made to locate subjects to determine and report their ongoing status. This includes follow-up with persons authorized by the subject as noted above. Lost to follow-up is defined by the inability to reach the subject after a minimum of 2 documented phone calls, faxes, or e-mails as well as lack of response by the subject to 1 registered mail letter. All attempts should be documented in the subject's medical records. If it is determined that the subject has died, the site will use permissible local methods to obtain the date and cause of death. If the investigator's use of a third-party representative to assist in the follow-up portion of the study has been included in the subject's informed consent, then the investigator may use a Sponsor-retained third-party representative to assist site staff with obtaining the subject's contact information or other public vital status data necessary to complete the follow-up portion of the study. The site staff and representative will consult publicly available sources, such as public health registries and databases, in order to obtain updated contact information. If, after all attempts, the subject remains lost to follow-up, then the last-known-alive date as determined by the investigator should be reported and documented in the subject's medical records.

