Subjects may withdraw from the study at any time at their own request, or they may be withdrawn at any time at the discretion of the investigator or Sponsor for safety or behavioral reasons, or the inability of the subject to comply with the protocol-required schedule of study visits or procedures at a given study site.

If a subject does not return for a scheduled visit, every effort should be made to contact the subject. All attempts to contact the subject and information received during contact attempts must be documented in the subject's medical record. In any circumstance, every effort should be made to document subject outcome, if possible. The investigator should inquire about the reason for withdrawal, request that the subject return all unused investigational product(s), if applicable, request that the subject return for a final visit, if applicable, and follow up with the subject regarding any unresolved adverse events.

If a subject withdraws prior to Day 113, the following assessments should be completed:

- Obtain information regarding the use of concomitant medication and the occurrence of adverse events;
- Collect information on new bleeding episodes;
- Monitor infusion/injection site reactions;
- Assess symptoms by spontaneous reporting of adverse events and by asking the subjects to respond to a non-leading question such as "How do you feel?"
- Conduct a limited physical examination at the discretion of the investigator, if clinically indicated, to assess changes from baseline/previous visits of any ongoing symptoms;
- Confirm proper contraception is being used;
- Collect the subject's diary and review with the subject/caregiver, if applicable, including information about study compliance, bleeding assessments (including site and traumatic/spontaneous) and injection site reactions;
- Collect weight;
- Obtain pulse rate, respiratory rate, oral temperature, and supine blood pressure;
- Collect urine for urinalysis for shipment to the study central laboratory.
- Collect blood samples for the following for shipment to the study central laboratory:
  - Serum chemistry;
  - Hematology;

- TFPI level;
- PT/INR;
- aPTT;
- Fibrinogen;
- TGA;
- PF1+2;
- D-dimer;
- dPT;
- PK blood sampling;
- Immunogenicity (ADA, NAb);

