- Subjects with positive ADA or NAb may be required to attend additional, unscheduled follow-up visits. Extended follow-up visits every 2 weeks for up to 3 months, including vital signs, immunogenicity, AE and concomitant medication assessments, may be performed.
- Subjects who are ADA or NAb positive, who have also been administered FVIIa or FEIBA, should be followed at all remaining clinic visits up to Day 113 or up to 3 months following positive ADA/NAb results, whichever is longer.

If the subject withdraws from the study, and also withdraws consent for disclosure of future information, no further evaluations should be performed, and no additional data should be collected. The Sponsor may retain and continue to use any data collected before such withdrawal of consent.

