### **8.2. Reporting Period**

For SAEs, the active reporting period to Pfizer or its designated representative begins from the time that the subject provides informed consent, which is obtained prior to the subject's participation in the study, ie, prior to undergoing any study-related procedure and/or receiving investigational product, through and including 28 calendar days after the last administration of the investigational product. SAEs occurring to a subject after the active reporting period has ended should be reported to the Sponsor if the investigator becomes aware of them; at a minimum, all SAEs that the investigator believes have at least a reasonable possibility of being related to investigational product are to be reported to the Sponsor.

AEs (serious and non-serious) should be recorded on the case report form (CRF) from the time the subject has taken at least 1 dose of investigational product through the subject's last visit.

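### After a dose-limiting toxicity, Section 3.3 allows adverse event monitoring to end before Day 113 once the toxicity has resolved and drug is eliminated, which conflicts with the endpoint window and the Schedule of Activities

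*Protocol*

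**What the plan says.** **The DLT rule.** Under Protocol Section 3.3, Dose Modifications, a subject with a DLT is taken off drug. From then on, this subject "will be followed for adverse event monitoring until resolution of the respective toxicity and elimination of study drug or the end of the study". The sentence pairs the second limb (Day 113) with resolution or stabilization of the toxicity, and the earlier limb governs. It does not define elimination, and it does not say whether scheduled visits continue.

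**Other subjects who stop drug.**
- APCC recipients (Section 5.7.1): "These subjects should be followed at all remaining clinic visits up to Day 113 to monitor for adverse events and any additional safety concerns".
- Subjects who ask to stop (Section 6.4): "Subjects who request to discontinue study treatment will remain in the study and must continue to be followed for protocol specified follow-up procedures", unless they withdraw consent to contact.
- ADA/NAb-positive subjects who also received FVIIa or FEIBA (Section 6.4) "should be followed at all remaining clinic visits up to Day 113 or up to 3 months following positive ADA/NAb results, whichever is longer".

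**Rules that give partial cover.**
- Section 1.3.2: coagulation laboratory monitoring "until at least 28 days have passed since the final administration".
- Section 8.2: active SAE reporting "through and including 28 calendar days after the last administration of the investigational product", with related SAEs still reportable later. All adverse events are recorded on the CRF up to the last visit.
- Section 6.4: "If a subject withdraws prior to Day 113, the following assessments should be completed", a list that includes laboratory tests and ADA/NAb.
- Section 3.2: a subject with a treatment-related event "will continue to be followed through resolution or stabilization of the event as agreed upon by the investigator and Sponsor".

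**The window.** Sections 2.2.1 and 2.2.2 set the primary safety endpoints and the ADA/NAb endpoint from Day 1 to Day 113. Table 2 carries adverse event monitoring through Day 85 and again at Day 113. Table 2 and Section 6.3.1 list discharge only at Day 113.

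**The concern.** Safety is the primary objective, and each cohort has 6 subjects, so one DLT subject is 1/6 of a cohort. Read literally, Section 3.3 permits the shortest safety follow-up in the subjects who showed toxicity. The early limb can plausibly come first. Appendix 2 counts as DLTs some findings that may pass quickly, such as temperature above 38.5°C, pulse above 120 or a systolic change of 30 mm Hg. Once such a finding has resolved, only elimination delays the end of monitoring.

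At stake are late laboratory, vital sign and ADA/NAb data and non-serious adverse events, since CRF recording runs to a last visit that is not fixed for this subject. Section 3.1 allows replacement only after withdrawal for reasons other than safety, so if the subject is withdrawn for the toxicity, a replacement would not make up these data.

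**Working it through.** The plan gives no figure to reproduce. The check is whether the early limb can fall before Day 113, whether another rule overrides it, and how many visits that would affect.

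**1. The rule as logic.** End of monitoring = the earlier of A and B.
- A = the later of (resolution, elimination).
- B = the later of (Day 113, resolution or stabilization), which is never before Day 113.

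Monitoring can therefore end early exactly when A falls before Day 113.

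**2. Does another rule close it?** Section 6.4 on requested discontinuation covers subjects who ask; a DLT stop is imposed. Section 5.7.1 covers APCC recipients. The ADA/NAb rule needs both positivity and FVIIa or FEIBA. Section 1.3.2 covers coagulation laboratory endpoints only. Section 8.2 extends SAE reporting, not visits. The withdrawal assessments are a single set, and apply only if the end of monitoring counts as withdrawal. Section 3.2 stops at resolution or stabilization. None clearly carries routine visits to Day 113 for a resolved DLT.

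**3. When could A occur?** Assumption: elimination = 5 × half-life, using Table 3 (single doses, healthy subjects).
- 300 mg SC (n=3): 5 × 65.77 / 24 = 13.7 days.
- 440 mg IV (n=5): 5 × 79.46 / 24 = 16.6 days.
- 300 mg SC, Japanese (n=2): 5 × 98.35 / 24 = 20.5 days.

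The upper end is 28 days, if the 28-day statements are taken to bind. That is a best case for chemistry, vital signs and ADA/NAb, which those statements do not cover.

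**4. Visits at risk, if scheduled visits do not continue.** End day = last dose day + 13.7 to 28. A visit counts only if its whole window lies later (nominal day minus window > end day). Safety-laboratory visits after Day 1, with windows: 8 (±1), 15, 22, 29, 57, 85 (each ±2), 113 (±7). ADA/NAb: 15, 29, 57, 85, 113.

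| Last dose | End day, five half-lives | End day, 28 days | Days before Day 113 | Laboratory visits | ADA/NAb visits |
|---|---|---|---|---|---|
| Day 1 | 14.7–21.5 | 29 | 84–98 | 3–5 | 3–4 |
| Day 29 | 42.7–49.5 | 57 | 56–70 | 2–3 | 2–3 |
| Day 57 | 70.7–77.5 | 85 | 28–42 | 1–2 | 1–2 |
| Day 78 (SC only) | 91.7–98.5 | 106 | 7–21 | 0–1 | 0–1 |

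Example, last dose Day 1. An end on Day 14.7 leaves Days 22, 29, 57, 85 and 113 (5 laboratory visits) and Days 29, 57, 85 and 113 (4 ADA/NAb). An end on Day 29 leaves Days 57, 85 and 113 (3 and 3).

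**5. Adjustments.**
- Section 3.3 requires review of available data through at least Day 29 in 6 of 6 subjects before progression to a higher or untested regimen. Where that applies, Days 22 and 29 would be expected for a Day 1 DLT, leaving 3 and 3.
- If the withdrawal set applies, one set returns: 2–4 laboratory and 2–3 ADA/NAb for Day 1, none lost for Day 78.

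**6. Off-drug observation against completers.** SC: 113 − 78 = 35 days, against about 14–28, so 7–21 days less. IV: 113 − 57 = 56 days, against about 17–28, so 28–39 days less.

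**The case against.** The strongest reply is that the Schedule of Activities is the default. Section 3.3 removes the subject from treatment only, nothing says that visits stop, and discharge appears only at Day 113. On this reading, Section 3.3 sets how long the toxicity is followed, on top of the schedule. This is reasonable and may be what the sponsor intends. It stands to this extent: a reader might infer that DLT subjects leave the study at resolution, and the documents do not say so. It does not remove the problem. Section 3.3 gives adverse event monitoring its own earlier end, while Section 5.7.1 spells out continuation for another off-drug group, so two sites could act differently in good faith.

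The second reply is that the durations are assumptions. That stands in full. The half-lives rest on 2 to 5 healthy subjects per group, and Table 3 has none for 450 mg SC or 1000 mg IV. Half-life rose with dose, and the predicted steady-state Cmax at 300 mg SC weekly is 77,000 ng/mL (Table 4) against 16,490 ng/mL after one dose (Table 3). Elimination after repeat dosing is therefore probably slower and the gap smaller. If sites confirm elimination from scheduled PK samples, those after Day 33 fall only on Days 57, 85 and 113, which narrows it further.

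Third, safety is summarized descriptively, and any missing data would fall after both resolution and elimination. That limits the consequence but does not reconcile the sections.

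**Conclusion.** The conflict between Section 3.3 and both the endpoint window and the Schedule of Activities is real and worth correcting as a cheap improvement. Its effect is incomplete late safety and immunogenicity data in a few subjects. The size runs from 3–5 laboratory and 3–4 ADA/NAb visits (last dose Day 1; about 3 and 3 where the Day 29 review operates) to 0–1 of each (last dose Day 78). This assumes that sites stop scheduled visits and that elimination takes five single-dose half-lives, or 28 days at most. It is smaller if the withdrawal set is collected or drug clears more slowly after repeat dosing.

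Three stronger inferences are not supported:
- That monitoring may end on resolution alone. Elimination is also required.
- That the toxicity or the subject drops out of the analysis. The DLT counts for escalation, and data already collected stay in the Safety Analysis Set.
- That a gap of 12 to 14 weeks is typical. It is the extreme case, a last dose on Day 1.

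**What to change.** In Section 3.3, Dose Modifications, replace the early-exit limb with wording such as:

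> A subject discontinued from investigational product for a dose-limiting toxicity remains in the study and is followed at all remaining scheduled visits through Day 113, with the safety, laboratory, vital sign and ADA/NAb assessments in the Schedule of Activities; unresolved toxicity is followed to resolution or stabilization.

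This extends the Section 5.7.1 approach to DLT subjects and is more specific about assessments than that section. Elimination then needs no definition.

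The cost is one sentence in an amendment. The visits and samples are already scheduled, so the added burden is attendance and blood draws for a few subjects off drug. One consequence needs a matching line in the SAP: Section 5.2.3 uses log time on study as the offset for bleed counts, so it should state that off-drug days after a DLT are not counted as treated time, and that bleeds on those days are handled the same way.
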